We will measure EtG and EtS in urine. If new urine biomarkers for ethanol are discovered while we are running the protocol, we may measure those as well. We will also measure other substances in the urine samples (such as creatinine) that provide quality assurance for the biomarker measurements.

D. Study Objectives

The objective of this study is to test a novel behavioral intervention, US memory retrieval-extinction, for efficacy in attenuating cue-induced alcohol craving and drinking in problem drinkers.

Our co-primary objectives are to determine whether the retrieval-extinction procedure reduces (1) self-reported craving in response to alcohol cues presented in the laboratory and (2) EMA reports of alcohol craving and drinking in daily life. We have designated these as co-primary outcomes because laboratory data are more mechanistically informative and field data are more clinically relevant. We will assess self-reported craving during laboratory sessions conducted within and between four retrieval-extinction sessions, and then in tests for Pavlovian renewal and reinstatement that will follow the final retrieval-extinction session. We will assess changes in EMA reports before, between, and after the laboratory sessions. We hypothesize that, compared to the control groups, individuals receiving alcohol US retrieval-extinction will show reductions in craving (and possibly in drinking) over time. If we detect our hypothesized effects on the EMA measures alone, we will consider that sufficient evidence for the efficacy of the procedure. If we detect our hypothesized effects on the laboratory measures alone, we will consider that suggestive of possible efficacy, indicating that the procedure might need to be administered more intensively in future work.

Abbreviated Title: Lab/GMA drinking

Version Date: 2/16/2022

Our secondary objectives are to test the effects of the retrieval-extinction procedure on (1) self-reported alcohol craving and drinking at the 30-day follow-up by telephone, (2) physiological responses to alcohol cues in the laboratory, and (3) biomarkers for alcohol consumption. We hypothesize that, compared to control groups, individuals receiving US retrieval-extinction will: report less alcohol craving and drinking at the 30-day follow-up telephone contact; have a reduction in physiological responses to cues; and have a reduction in biomarkers for alcohol consumption.

E. Study Design and Methods

1. Study overview

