The session will last approximately one hour. At the beginning and end of the session, participants will rate their alcohol craving using a one-item alcohol craving VAS adapted from that of MacKillop and Lisman (2008): “I want an alcoholic drink right now”; 0 = “I don’t want an alcoholic drink at all,” 100 = “I *really* want an alcoholic drink.” This urge scale will be used to measure craving during the extinction sessions. This same scale will be used for measuring craving during the extinction procedures, renewal test, and reinstatement conducted subsequently (described below). We are using a one-item VAS measure for craving because, in our prior studies, we have usually been better able to detect manipulation effects with these straightforward measures than with multi-item assessments of craving, and there may be good theoretical reasons for that (McGrath, 2005). We will measure craving for soft drinks using a similar VAS except references to alcoholic drinks are replaced by references to soft drinks. The alcohol and soft-drink craving scales are provided in the Appendix.

Before the end-of-session rating, participants will be given a 10-minute period with instructions to initiate progressive muscle relaxation and to focus on deep breathing. The relaxation procedure will be repeated until participants report not feeling stress and craving greater than pre-interview levels. Participants will then be discharged.

Initiation of GMA: During Session 1, participants will each be issued a smartphone. We will show them how to use the phone for EMA entries and ask them to make several practice entries (which will not be used in data analysis). We will explain the automatic collection of location information by the smartphone’s GPS chipset. They will be shown how to charge the phone. They will be asked to keep the phone on and to carry it at all times.

GMA data will be transferred wirelessly from participants’ phones to servers located at the NIDA BRC under a secure communications system developed by the NIDA Biomedical Informatics Section. Transfers will be scheduled to occur automatically at least twice a day. Participants will not have to visit the laboratory for these data transfers. If the remote transfers fail, we can manually initiate a wireless transfer when participants make their regularly scheduled laboratory visits. If that fails, we will swap out the participant’s phone so that the NIDA Biomedical Informatics Section can try to recover the data.

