reappear because the US has been reintroduced to create a “priming” effect. Each participant will undergo both the renewal and reinstatement procedures, in that order, in one session.

Renewal-test procedures: We will use a within-participant renewal procedure based on that of Thewissen and colleagues (2006), who studied renewal of cue-elicited cigarette craving. Participants will be given alcohol cues in both the same room in which they underwent retrieval-extinction (the extinction-concordant room) and a different room (an extinction-discordant room). The identities of the rooms, and the order of their presentation in the renewal test, will be counterbalanced across participants within each group. Renewal is indicated by significantly greater cue reactivity in the extinction-discordant room than the extinction-concordant room. This is a proxy measure for the clinical problem of patients’ renewed craving after returning from the extinction setting to an outside environment (although, in our protocol, we will be attempting to assess that directly with GMA as well).

In the renewal procedure, participants will not be given an experimental beverage. Instead, in each room, they will rate their alcohol and soft-drink craving before and after a single block of alcohol cues, to be presented the same way as in the extinction sessions. In each room, physiological monitoring will begin 10 minutes before cue presentation and will continue for 5 minutes after the end of the craving ratings. This abbreviated schedule, compared to physiological monitoring used during the extinction procedure, is needed to allow for the tests to be completed in a timely manner with participants travelling between the two experimental rooms and spending time in a third, neutral room of the laboratory in between (described below).

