BAC will be checked at the start of the session and will need to be 0.00% to proceed. Between their time in the first and second rooms, participants will spend 30 min in a third, neutral room and will be given a distractor: they will watch a series of short videos that have been screened for emotional and drug-use content and afterwards answer brief questions about their content. Videos will be drawn from the popular (approx. 3 million subscribers) online science and technology video series SciShow. The list of videos to be used and the list of questions to be asked are provided in the Appendix. The distractor is intended to limit carryover effects from cue presentation in the first room to the second (Reynolds & Monti, 2013). After completion of the renewal test, to limit carryover from the renewal procedure to the subsequent reinstatement procedure, participants will be returned to the neutral room for 30 min to complete the distractor task for a second time with a fresh video.

Reinstatement-test procedure: We know of no prior explicit demonstrations of the reinstatement of extinguished drug-conditioned responses in human laboratory studies, but reinstatement has been documented in human studies of fear conditioning (Haaker et al., 2014).

Abbreviated Title: Lab/GMA drinking

Version Date: 2/16/2022

After the second distractor, all participants will be returned to the extinction-concordant room for the reinstatement procedure. Physiological monitoring will begin, and 10 min later, participants will rate their alcohol and soft-drink craving. They will then be given their experimental soft drink, which they will have 40 min to drink. 30 min later, they will again rate their alcohol and soft-drink craving. Then, they will be given their experimental alcoholic beverage, which they will have 40 min to drink. 30 min later, their BAC will be measured by breathalyzer, and they will again rate their alcohol and soft-drink craving. Reinstatement is indicated by greater craving after the alcoholic beverage than after the soft drink.

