Stored biological specimens will be kept in a secure freezer in the Archway's NIDA freezer room until they are analyzed (BRC building; room 01B405). Specimens that are not used up in the analyses will be saved, but will not be used for any purpose not described in the protocol without prior IRB approval.

Urine samples will be kept in a secure freezer in the Archway's NIDA freezer room until they are analyzed (BRC building; room 01B405) and tracked by barcode. Those that are not used up in the analyses will be disposed of after the study. They will not be used for any purpose not described in the protocol without prior IRB approval. Any unplanned loss or destruction of the samples will be reported by the PI to the IRB.

I. Statistical Analysis

1. Outcome measures

Primary: (1) self-reported alcohol craving during the laboratory sessions, (2) GMA reports of alcohol craving and drinking.

Secondary: (1) self-reported alcohol craving and drinking at the 30-day follow-up, (2) heart rate during laboratory sessions and GMA collection periods, and (3) biomarkers for drinking, detected in urine samples collected during laboratory sessions.

2. Analysis of study outcomes

There are two ways in which we are performing multiple tests of statistical significance. First, we have two co-primary outcomes: a lab measure and an ambulatory measure. This design is actually conservative, because we will not consider US retrieval-extinction fully successful if it affects only the first outcome (protection from renewal/reinstatement in a lab setting) without affecting the second outcome (changes in daily-life behavior).

Second, we need to compare our experimental group to each of the two control groups—we expect the control groups to be similar to each other. If the experimental group differs from only one of the control groups, we will have to conclude that the effect of US retrieval-extinction did not actually require both retrieval and extinction, and thus worked via some unexpected mechanism. Although we might ultimately need to perform the two comparisons separately to explore unexpected findings, our main planned analysis is a single test of the joint hypothesis that the experimental group differs simultaneously from both control groups.

Our specific tests will be as follows.

Abbreviated Title: *Lab/GMA drinking*

Version Date: 2/16/2022

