Co-primary outcome 1: Protection from renewal/reinstatement of craving in session 6. We will analyze this in a linear regression model so we can control for a continuous covariate: each participant's mean level of craving in prior sessions (along with any person-level covariates that improve the fit of the model). To test the joint hypothesis that the extinction-retrieval group differs simultaneously from both control groups, we will dummy-code the 3-level predictor Group using two variables: Control Group A (0,1) and Control Group B (0,1), thereby making our intervention group the reference level. We will then perform a Wald test of the joint significance of the two Control Group predictors, maintaining an alpha of .05.

The dependent variable will be operationalized in terms of participants' ratings of alcohol craving in the renewal procedure and the reinstatement procedure from session 6. For each participant, we will generate a summary measure of renewal susceptibility (or, for separate analyses, reinstatement susceptibility) using within-session scores from session 6. For renewal, the score will be calculated as:

(pre-to-post-cue craving change in discordant room) *minus*
 (pre-to-post-cue craving change in concordant room)

For reinstatement, the score will be calculated as:

(pre-to-post-cue craving change after alcohol) *minus*
 (pre-to-post-cue craving change after soft drink)

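### Does the unnamed starting rating in the reinstatement score leave a co-primary laboratory measure undefined?

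*Combined protocol and SAP*

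**What the plan says.** Section I.2, under co-primary outcome 1, defines two session 6 scores for separate analyses. The renewal score is the pre-to-post craving change in the discordant room minus the same change in the concordant room. The reinstatement score keeps that form: the change after alcohol minus the "pre-to-post-cue craving change after soft drink".

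For renewal, section E.2.c supplies the ratings that this form needs: "in each room, they will rate their alcohol and soft-drink craving before and after a single block of alcohol cues". Each room has its own pair, so there are four ratings.

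For reinstatement, the same section gives only three:

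- **B**, before either drink: "Physiological monitoring will begin, and 10 min later, participants will rate their alcohol and soft-drink craving".
- **S**, after the soft drink and directly before alcohol: "30 min later, they will again rate their alcohol and soft-drink craving. Then, they will be given their experimental alcoholic beverage".
- **A**, 30 minutes after the time allowed for the alcoholic drink.

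Section E.2.c then states the criterion: "Reinstatement is indicated by greater craving after the alcoholic beverage than after the soft drink". The instrument is the 0–100 craving scale introduced for Session 1 (section E.2.a): "This same scale will be used for measuring craving during the extinction procedures, renewal test, and reinstatement conducted subsequently".

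Two statements limit the weight of the laboratory outcome. Section I.2 says "we will not consider US retrieval-extinction fully successful if it affects only the first outcome", and section D says "If we detect our hypothesized effects on the laboratory measures alone, we will consider that suggestive of possible efficacy".

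**The concern.** A difference of two changes needs a starting point for each. The soft-drink change can start only from B. The alcohol change could start from B, as a common baseline, or from S, the last rating before the alcohol. The parallel with renewal, where each room has its own starting rating, points to S. The criterion in section E.2.c points to B.

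If the choice were truly open, two analysts could compute different values of a co-primary variable, sometimes of opposite sign, in a study that is not blinded. The joint Wald test has no direction of its own, so benefit or harm is read from the two Control Group coefficients, and these too could change sign. The planned covariate does not settle the matter, because it is mean craving in prior sessions and not B.

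**Working it through.** **The plan's own figure.** Section J gives power .80 for f² = 0.13 with 75 participants. Two tested predictors out of three give 2 and 75 − 3 − 1 = 71 degrees of freedom, and the noncentrality is 0.13 × 75 = 9.75. The noncentral F distribution then gives power 0.787; exactly .80 needs f² = 0.134, which rounds to the stated value. The figure is reproduced. It does not separate the two readings, because f² is expressed relative to the residual variance of whichever score is analysed.

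**The two readings.**

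- Common baseline: (A − B) − (S − B) = A − S.
- Rating just before each drink: (A − S) − (S − B) = A − 2S + B.
- Difference: (A − S) − (A − 2S + B) = S − B.

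**Comparison with section E.2.c.** The criterion there is A > S, that is A − S > 0. The first reading is this criterion; the second is not. The Study Timeline table in section E.2 marks no cue script for reinstatement, so the words about a pre-to-post-cue change have no scripted cue block to refer to. The simplest explanation is that the renewal wording was carried over.

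**One participant.** With B = 30, S = 45, A = 55, the first reading gives 55 − 45 = +10 and the second 55 − 90 + 30 = −5. A positive A − S turns negative exactly when 0 < A − S < S − B.

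**The planned test.** It concerns group coefficients, not the sign of anyone's score. With the same participants and covariates, least squares is linear in the outcome, so

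coefficient for (A − 2S + B) = coefficient for (A − S) − coefficient for (S − B).

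A soft-drink change shared by all groups goes into the intercept and leaves the group coefficients alone. Two sets of hypothetical means (B, S, A) show this.

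- *Soft-drink change differs.* Experimental 40, 40, 50; both controls 40, 50, 65. On A − S: 10 against 15, control minus experimental +5. On A − 2S + B: 50 − 80 + 40 = 10 against 65 − 100 + 40 = 5, a difference of −5. The gap between the answers is 5 − (−5) = 10, the group difference in S − B (10 against 0).
- *Soft-drink change shared.* Give the experimental group the same 10-point soft-drink rise and keep its 10-point alcohol rise: 40, 50, 60. On A − S: 10 against 15, difference +5. On A − 2S + B: 60 − 100 + 40 = 0 against 5, difference +5. The answers agree.

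**Drift.** The soft drink always comes first, so A − S keeps any drift between S and A. If craving drifts by d per step and alcohol adds r, then S = B + d and A = B + 2d + r. Hence A − S = d + r and A − 2S + B = r. The second score removes linear drift from each participant's value. In the group comparison, a d common to all groups drops out of both scores.

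**The case for a change.** The strongest counter-argument is that B cancels under A − S, so writing two changes would serve no purpose; the author of section I.2 may therefore have meant B to count. Nor can equal soft-drink changes be assumed. Control group A drank the soft drink at retrieval in four sessions while the other two groups drank alcohol, so the groups reach session 6 with different histories.

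The choice can also affect precision. If the three ratings have equal variance and equal correlations, A − 2S + B has 6/2 = 3 times the variance of A − S. If, in addition, the group effect falls on A alone, f² drops from 0.13 to 0.13/3 = 0.043 and power from 0.787 to about 0.33. With autoregressive correlations of 0.5 to 0.9 the variance ratio is 2.5 to 2.1.

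Part of this stands. Section I.2 is incomplete on its own, S − B could differ between groups, and the two scores would not have the same standard error. But the redundant form is explained by the copied renewal template, whereas section E.2.c defines reinstatement specifically for this test. The premise in section E.1 is that soft drinks are inactive for alcohol craving, and section E.2.b screens out caffeinated drinks and the participant's usual mixers. That does not guarantee equal changes, but it makes a large group difference less expected. The documents give no standard deviations or correlations for craving ratings, so the power loss is illustrative. It also counts against A − 2S + B, the reading that section E.2.c does not support. As for choosing after seeing results, the criterion is already in the protocol, so a departure from it would be visible.

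**Conclusion.** The concern identifies a real gap in wording but does not call for a change. Sections I.2 and E.2.c describe the same test, and only A − S satisfies both, so an analyst can fill the gap sensibly. The alternative is no clear improvement: it removes linear drift from individual scores, but it departs from the stated criterion and, under the correlation structures tried, has the larger variance.

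The size of the issue is exact in form and unknown in amount. The two readings move each group coefficient apart by the adjusted group difference in S − B. That is nothing if the soft-drink change is equal across groups, and it can reverse direction if the change differs enough, as in the hypothetical 10-point case. The documents do not show how often, or whether, that would happen.

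The conclusion assumes that the two sections are meant to describe one quantity, and that the comparison of readings uses the same participants and covariates. The consequence is limited in any case: renewal is scored separately, and a laboratory effect without a daily-life effect would not be called full success.
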